# 4.14.3 Vital Sign Measurements

Vital signs will include systolic blood pressure (mmHg), diastolic blood pressure (mmHg), respiratory rate (breaths/min), heart rate (beats/min), and body temperature (°C). Pulse oximetry (to measure peripheral capillary oxygen saturation [SpO2] (%) will also be summarized. Vital sign observed and change from baseline will be summarized over scheduled visits.

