## **3.2.** Subject Exclusion Criteria

Subjects will not be eligible to participate in the study if they meet any of the following criteria:

- 1. Use of, or anticipated need for, invasive mechanical ventilation, cardiopulmonary bypass, hemodialysis, or extracorporeal membrane oxygenation; or subjects who are not expected to survive the current illness;
- 2. Subjects who have a medical history or a concurrent illness that in the opinion of the Investigator, might confound the results of the study or pose an additional risk in administering study drug to the subject, or that could prevent, limit, or confound the protocol-specified assessments. Examples include liver or renal insufficiency; significant cardiac, vascular, pulmonary, gastrointestinal, endocrine, neurologic, hematologic, rheumatologic, or metabolic conditions;

- 3. Subjects who are considered unable to take study drug orally,
- 4. Subjects who have received blood products within 6 months of study drug administration;
- Subjects with underlying immune deficiency (e.g., from confirmed human immunodeficiency virus infection or use of an immunosuppressive medication except immunoglobulin A deficiency);
- 6. Subjects who received (within 12 months before Screening) or who are currently on a waiting list for a bone marrow, stem cell, or solid organ transplant, or who received radiation or chemotherapy (within 12 months before screening);
- 7. Subjects who have had major surgery in the 6 weeks before randomization;
- 8. Subject receiving chronic oxygen therapy at home before admission;
- 9. Subjects who are being breastfed by a mother taking any of the excluded medications as noted in Section 5.9 (Prohibited Medication);
- 10. Subjects whose mother received an RSV vaccination while pregnant with the subject if they were born at term (≥37 weeks of gestation) and are less than 12 months of age;
- 11. Receipt of systemic antiviral, antifungal, or antimycobacterial therapy within 7 days of Screening;
- 12. Subjects who received systemic medications other than corticosteroids (either chronically [more than 14 days] or within 21 days before randomization) that are known to modulate the host's immune response or increase viral shedding, such as immunomodulatory therapies;
- 13. In Part 2, subjects dosed with an investigational or approved medication that is intended to prevent or treat RSV infection within the following times before the first dose of study drug:
  - ribavirin: 35 days,

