# 8.4. Vital Sign Measurements

Vital signs include heart rate, respiratory rate, systolic and diastolic blood pressure, body temperature, and pulse oximetry (to measure peripheral capillary oxygen saturation [SpO2]).

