# 8.9. Clinical Evaluation

Clinical evaluation will include but not be limited to the following evaluations of the clinical course of RSV infection:

• Vital signs (respiratory rate, heart rate, systolic blood pressure, diastolic blood pressure, SpO2, and body temperature);

- Level of care (e.g., ICU, translational care unit, ward floor, home);
- Duration of hospitalization if hospitalized;
- Incidence of MAARI including hospitalizations, outpatient clinic visits, emergency department visits, and telephone visits due to acute respiratory infection;
- Requirement for and duration of oxygen supplementation/noninvasive mechanical ventilation support (e.g., nasal cannula, face mask, continuous positive airway pressure) and/or invasive mechanical ventilation support (e.g., endotracheal-mechanical ventilation or mechanical ventilation via tracheostomy);
- Requirement for hydration and feeding by IV catheter/nasogastric tube.

On Day 1, these assessments must be done predose.

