#### 11.5.5. Vital Sign Measurements

The incidence rate of subjects with treatment-emergent vital sign changes at any post-Baseline visit will be summarized. Specific criteria for the classification of treatment-emergent will be documented in the SAP. Vital sign observed, change, and percentage change will be summarized by treatment over visits. Oxygen saturation (SpO2) measurements will be summarized by visit and treatment.

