# Secondary Endpoints

• Safety and tolerability of EDP-938 compared to placebo as assessed by, but not limited to, AEs, vital signs, and clinical laboratory results;

- AUC for RSV RNA viral load measured in nasal swab samples by RT-qPCR;
- Proportion of subjects with RSV RNA viral load below the LOD in subjects receiving EDP-938 compared to placebo;
- Time to RSV RNA viral load being undetectable;
- PK parameters of EDP-938 including AUC and predose concentrations;
- Time to discharge for hospitalized subjects;
- Time to use of oxygen for hospitalized subjects who are not receiving oxygen at the time they receive the first dose of study drug;
- Proportion of hospitalized subjects requiring oxygen supplementation or have an increased oxygen requirement;
- Time to mechanical ventilation for hospitalized subjects;
- Proportion of hospitalized subjects requiring mechanical ventilation;
- Deaths among hospitalized subjects;
- Time to hospitalization for initial outpatients who are subsequently hospitalized;
- Proportion of outpatients who are subsequently hospitalized or died;
- Time to resolution of symptoms for outpatients who are not hospitalized.

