- Time to confirmed undetectable RSV RNA viral load (days) is defined as the time between the date of first dose to the first 2 consecutive post-baseline time points of

achieving RSV RNA viral load TND. Subjects with baseline RSV viral load TND will be excluded from the analysis.

Frequency counts and percentages of subjects by end of study (Day  $28 \pm 4$ ), and their respective 95% CIs will be reported using Clopper Pearson CI methods for the following endpoints summarized using the Efficacy Population.

- Proportion of hospitalized subjects requiring oxygen supplementation or have an increased oxygen requirement.
  - Subjects who are hospitalized at randomization and/or during study are included. The
    proportion will be defined by the number of subjects who develop a new requirement for
    oxygen supplementation or new increase(s) in oxygen requirements after the first dose of
    study drug, based on the response of "yes" to the "is this an increase of oxygen
    supplementation compared to previous use?" question on the Oxygen Supplementation
    CRF.
- Proportion of hospitalized subjects requiring mechanical ventilation
  - Subjects who are hospitalized at randomization and/or during study are included. The proportion will be defined by the number of subjects who developed a new requirement for mechanical ventilation after the first dose of study drug. Subjects on mechanical ventilation prior to the first dose of study drug are excluded from analysis.
- Deaths among hospitalized subjects
  - Subjects who are hospitalized at randomization and/or during study are included.
- Proportion of outpatients who are subsequently hospitalized or died
  - $\circ$  Subjects who are not hospitalized at randomization are included.
- Proportion of outpatients who died
  - Subjects who are not hospitalized at randomization are included.

The following endpoints will be summarized using the Efficacy Population. The summary statistics will include, at a minimum, the number of non-missing measurements, mean, standard deviation, median, minimum, 25th percentile, 75th percentile, and maximum.

- Time to discharge for hospitalized subjects
  - Time to first hospital discharge for subjects who are hospitalized at randomization will be defined as the time between the first dose of study drug and the first date of discharge. For subjects with continuous hospitalization, the last date of discharge from the continuous hospitalization will be used.

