- Time to use of oxygen for hospitalized subjects who are not receiving oxygen at the time they receive the first dose of study drug
  - For subjects who are hospitalized at randomization, time to use of oxygen for hospitalized subjects not receiving oxygen at the time they receive the first dose, is

defined as the time between the date/time of first dose of study drug to the first date/time of receiving oxygen.

- Duration of oxygen use for hospitalized subjects
  - This analysis will include subjects who are hospitalized at randomization and received oxygen supplementation at any time after the first dose of study drug. The duration of oxygen use (days) is defined as the sum of each duration of oxygen use (days) that occurred from the first dose of study drug to the end of study. The duration of oxygen use for the initial hospitalization is calculated as date/time of the end of oxygen use – date/time of first dose of study drug. The duration of oxygen use for subsequent rehospitalization(s) is calculated as date/time of the end of oxygen use – date/time of the start of oxygen use for the rehospitalization. Missing start times will be imputed to 00:01. Missing end times will be imputed to 23:59.
- Time to mechanical ventilation for hospitalized subjects
  - This analysis will include subjects who are hospitalized at randomization and required mechanical ventilation at any time after the first dose of study drug. Subjects on mechanical ventilation before their first dose of study drug are excluded from analysis. Time to mechanical ventilation is defined as the date/time from the first dose of study drug to the first use of mechanical ventilation.
- Duration of mechanical ventilation for hospitalized subjects

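### The SpO2 summary in SAP 4.14.3 ignores supplemental oxygen, so observed values and change from baseline are confounded with oxygen support

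*SAP*

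**What the plan says.** **How SpO2 is measured and summarised.** Protocol 8.4 reads: "Vital signs include heart rate, respiratory rate, systolic and diastolic blood pressure, body temperature, and pulse oximetry". Neither that section nor the Schedule of Assessments asks for a room-air reading or for the support in use at the reading. SAP 4.14.3 says that pulse oximetry "will also be summarized. Vital sign observed and change from baseline will be summarized over scheduled visits". Protocol 11.5.5 adds only that SpO2 "measurements will be summarized by visit and treatment". SAP 4.5 sets the vital-sign analysis visits at Days 1, 3, 5, 9 and 14.

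**Who can be on oxygen.** The only oxygen-specific exclusion in Protocol 3.2 is "Subject receiving chronic oxygen therapy at home before admission". Use of, or anticipated need for, invasive ventilation is excluded separately. Acute oxygen for the current illness is not excluded. The time-to-oxygen endpoint in SAP 3.2.2 is limited to "hospitalized subjects who are not receiving oxygen at the time they receive the first dose of study drug", which presupposes that other children are already on oxygen.

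**What is recorded and reported about oxygen.** Protocol 8.9 collects "Requirement for and duration of oxygen supplementation/noninvasive mechanical ventilation support". SAP 4.13.4 names an Oxygen Supplementation CRF and reports "Proportion of hospitalized subjects requiring oxygen supplementation or have an increased oxygen requirement" and "Duration of oxygen use for hospitalized subjects", the latter from start and end date/times. SAP 4.13.5 repeats the secondary endpoints on pooled data. None of this is linked to the SpO2 table.

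**The concern.** A reading taken on oxygen reflects the child's lungs and the support being given. If supported and unsupported readings are averaged, a change between visits can come from either source. Two errors follow. A child who improves and is weaned may show a lower SpO2 than at baseline. A child who deteriorates and is started on oxygen may show no fall.

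Vital signs are named in the primary safety endpoint of Part 1 (SAP 3.2.1), and safety tables are produced for Part 1 on its own (SAP 4.1 and 4.14). The oxygen endpoints are listed for Part 2 and the pooled population, not among the Part 1 primary and secondary endpoints. The Part 1 SpO2 table therefore has no planned oxygen summary in those lists to be read with it.

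**Working it through.** **The plan's own figure.** Part 1: 2 age groups x 2 cohorts x 12 = 48. Part 2: 2 x 20 = 40. The total is 88, which agrees with the stated figure of about 90. Part 1 gives 2 x 2 x 8 = 32 EDP-938 and 2 x 2 x 4 = 16 placebo, taking the Cohort 1 split for Cohort 2 as well. Part 2 gives 2 x 16 = 32 and 2 x 4 = 8. The documents give no share of children on oxygen and no SpO2 distribution, so what follows rests on assumed values.

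**Model.** Observed SpO2 = room-air level + L if the child is on oxygen, where L is the number of points that oxygen adds. A constant L is a simplification. With share p_b on oxygen at baseline and p_v at the visit:

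mean observed change = mean room-air change - (p_b - p_v) x L

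The second term is the artefact.

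**Assumed inputs.** p_b 30-50%, p_v 10-20%, L 2 to 6 points.

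| p_b | p_v | L = 2 | L = 6 |
|---|---|---|---|
| 0.30 | 0.20 | -0.2 | -0.6 |
| 0.30 | 0.10 | -0.4 | -1.2 |
| 0.50 | 0.20 | -0.6 | -1.8 |
| 0.50 | 0.10 | -0.8 | -2.4 |

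The range is -(0.30 - 0.20) x 2 = -0.2 to -(0.50 - 0.10) x 6 = -2.4 points. True improvement adds back. If mean room-air SpO2 rises by 2 points, the observed mean change lies between 2 - 0.2 = +1.8 and 2 - 2.4 = -0.4.

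**One child.** A weaned child with a true gain of 2 shows 2 - L: 0 at L = 2, and -2 at L = 4. A child whose room-air level falls by 4 and who is given oxygen worth 4 points shows 0.

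**Between arms.** The artefact in the difference is L times the difference between arms in the net share coming off oxygen. If that share is equal, the artefact is zero. If it is 20 percentage points higher on EDP-938 (assumed), the arm difference shifts by 0.20 x 2 = 0.4 to 0.20 x 6 = 1.2 points against EDP-938.

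**Chance imbalance in Part 2.** If 30% are weaned in each arm (assumed), the standard error of the difference in that share is sqrt(0.30 x 0.70 x (1/32 + 1/8)) = 0.18. At L = 4 this is 0.18 x 4 = 0.7 SpO2 points, with no treatment effect on weaning.

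**The case against.** The strongest case against is that oxygenation is well covered elsewhere. SAP 4.13.4 reports new or increased oxygen need with confidence intervals, time to oxygen, duration of oxygen, new mechanical ventilation and deaths. SAP 4.13.5 repeats these on pooled data, so Part 1 children are counted there. Item 2 of both ReSVinet scores rises with oxygen therapy and again with positive-pressure support. Safety is descriptive, no formal testing is planned for Parts 1 or 2 (SAP 4.2), and the progression and stopping rules in Protocol 4.2.1 and 10.1 do not use mean SpO2. Individual data will be listed.

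Much of this stands, and it rules out three stronger readings that a reader might infer.

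- *That the summary reflects oxygen support as much as the child's condition.* That is a statement of quantity, and the documents give no oxygen prevalence. Readings from children on room air at both times are unaffected. Only Part 1 Cohort 1 Age Group 2, planned at 12 of 88, must be hospitalised.
- *That a child who is harmed and given oxygen would go unseen.* The SpO2 table could miss that child, but the oxygen endpoints and ReSVinet item 2 can show the move.
- *That the comparison with placebo is biased.* A shift common to both arms cancels; bias needs a difference in oxygen use.

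The objection does not remove the gap. The oxygen endpoints are proportions by end of study, times or durations, in hospitalised children of the Efficacy Population. They do not say who was on oxygen at the Day 3 or Day 5 reading, and they are not among the primary and secondary endpoints of Part 1. The CRF layouts, table shells and exploratory SAP section are not in the public text, so a split planned there cannot be excluded. The rule still belongs in SAP 4.14.3.

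**Conclusion.** The point holds as a confounding of one descriptive safety summary. Followed as written, SAP 4.14.3 mixes readings on and off oxygen, and its mean change from baseline cannot be read as a change in the child's own oxygenation. On the assumed inputs the artefact is -0.2 to -2.4 points before true improvement. Its size in this trial is unknown, because the documents give neither the shares on oxygen nor the points that oxygen adds. The comparison between arms is biased only to the extent that oxygen use differs by arm, through a treatment effect or through chance with 8 placebo children planned in Part 2. No tested endpoint is affected. The repair is inexpensive and worth making, most clearly for the Part 1 safety table.

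**What to change.** In SAP 4.14.3:

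1. Flag each SpO2 value as on support, room air or unknown, by comparing its date/time with the date/times on the Oxygen Supplementation CRF. The 00:01 and 23:59 defaults that SAP 4.13.4 uses for duration should not settle the status of a reading on that day; such a reading goes to unknown.
2. Summarise observed SpO2 by that status, and show n (%) on support at each visit by arm and part. This row makes a move onto oxygen visible.
3. Keep the overall change from baseline, with a footnote that it mixes oxygen states.
4. Change restricted to pairs with both readings on room air may be added as a supplementary row only. It selects on post-baseline oxygen status, which treatment may affect, and it omits children who move onto oxygen. It should carry that caveat and should not replace the overall row.

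The cost is SAP wording, one derived variable and extra table rows, from date/times that the SAP already uses. Nothing changes in how children are given oxygen. The downside is small cells: with 8 placebo children in Part 2, the assumed 10-20% on oxygen at a visit is 0.8 to 1.6 children. Some readings will be of unknown status.

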### 4.14.4 Electrocardiograms

Screening and Day 5 ECG data will be provided in data listings.

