# 8.5. Electrocardiograms

ECGs will be performed locally. A standard bedside 12-lead ECG machine that calculates heart rate and measures PR, QRS, QT, RR, and QT interval corrected for heart rate according to Fridericia (QTcF) intervals is strongly preferred but in cases where a 12-lead ECG is not possible or feasible, a 6-lead ECG may be used.

During the collection of ECGs, subjects should be calm, resting quietly, or sleeping if possible. If blood sampling and a nasal swab are scheduled for the same timepoint as ECG recording, those assessments should be done after the ECG.

The Investigator or designee should review the ECG for gross abnormalities and interval measurements of concern (absolute readings). The clinical interpretation by the Investigator or designee of the ECGs should be recorded on a hard copy of the ECG (ie, clinically significant or not clinically significant).

An ECG may be repeated at the discretion of the Investigator to address suspected errors in performance. Before dosing, the screening ECG must be reviewed to confirm that no clinically significant cardiac abnormalities are present.

All subjects with new abnormal cardiac laboratory values or abnormal ECG results after receiving study drug should have echocardiograms. For echocardiogram results, only clinically significant abnormalities should be recorded as AEs.

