# 8.12. Virology Assessments

Virology assessments and tests (see Table 3) will be performed using nasal swab samples collected at timepoints indicated in the SoA (Appendix 1) and as further described in the Laboratory Manual, including swab collection, sampling, and handling procedures.

Appropriate nasal swabs to assess RSV viral load (RT-qPCR and quantitative viral culture) and viral sequence should be taken by an appropriately trained study team member. At each visit, a single swab will be collected. Samples should be taken at approximately the same time each day before study drug administration. Nasal swabs should be frozen as soon as possible after being collected. The actual times of sample collection must be recorded in the source.

At Screening, RSV diagnosis will be based on an approved diagnostic assay performed locally. Other virology assessments will be sent to the central/reference laboratory.

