#### Non-hospitalized Subjects

- Visit 1: 3 hours postdose;
- Visit 3: predose;
- Visit 5: predose.

The predose samples should be collected at approximately the same time as the nasal swab sample(s). For the postdose sample collected on Day 1, a window of  $\pm 30$  minutes for the sampling time is acceptable. Actual date and time of PK sample collection will be recorded in the eCRF. In addition, the site should record the date and time of last dose taken before the PK sample collection. It is important that the date and time of each of PK blood sample are accurately recorded in the source documents.

The method of sampling for PK blood draws is at the discretion of the Investigator. Samples taken via peripherally inserted central catheter line, indwelling catheter access, individual peripheral phlebotomies, or an IV line (or comparable means of access) are preferred, however, in instances where samples are unable to be obtained from a second line, alternative methods (capillary blood sampling via heel sticks or finger sticks) are allowed.

Blood samples will be collected and processed to measure plasma concentrations of EDP-938 and its metabolites according to the procedures provided and/or approved by Enanta Pharmaceuticals, Inc. Additional details will be provided in the Laboratory Manual.

EDP-938 and its metabolites

in human

plasma will be quantified by high-performance liquid chromatography with tandem mass spectrometric detection. The method will be fully validated by assessment of precision, accuracy, sensitivity, and specificity of EDP-938 and its major metabolites by the laboratory selected by Enanta Pharmaceuticals, Inc.

Pharmacokinetic samples may be stored and used for future metabolite and/or further evaluation of the bioanalytical method. These data will be used for internal exploratory purposes and will not be included in the clinical study report.

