#### 11.5.6. Electrocardiograms

Screening and subsequent ECG data will be provided in data listings.

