Visit	Screening	V1	V2	V3	V4	V5	PT1	PT2	PT3 	and V4 assessments will be done at home. (X) is for V2 and V4 assessments for hospitalized subjects.
Dav	Day-1 to Day 1	1	2	$\frac{3}{(\pm 1)^4}$	4	5 (±1) EOT 	9 (±1)	14 (±2)	28 (±4) EOS 	Notes  : Protocol Section
Physical examination	X			X		х	X	X		Full PE at Screening. Subsequent PEs done at discretion of Investigator will be targeted to new signs and symptoms, including specific assessments of changes from previous status. Section 8.6
ECG	х					Х				12-lead ECG strongly preferred but where not possible, 6-lead ECG may be performed. If blood sampling and/or a nasal swab are scheduled for the same timepoint as ECG recording, those assessments should be done after the ECG. Section 8.5
Procedures					•					Residual samples from blood and/or nasal swab volume may be used for exploratory biomarker analyses. Section 8.14
Nasal swab		Х		Х		X	Х	X		Swab samples should be taken at approx. same time before study drug administration. One swab will be collected at each visit. Section 8.12
Blood sampling for clinical laboratory tests	Х	X*		X		х				Clinical laboratory tests include biochemistry, hematology, and cardiac biomarkers. All clinical laboratory tests that will be evaluated in the study are specified in Table 3. Evaluations will be conducted by local laboratories. *For subjects who have screening and randomization separated by more than 24 hours, blood sampling for clinical laboratory tests should be done predose on Day 1 for baseline values. This blood sampling does not need to be done for subjects who have randomization within 24 hours after screening because the screening clinical laboratory test results will be used as the baseline values. Section 8.11
Urinalysis	Х					X				Urine will be collected only from subjects who are either toilet trained and able to provide a specimen or are already catheterized or fitted with a urine collection bag, Section 8.11

Study Period	Screening 	Trea	tme	nt			Follow	-Up		For non-hospitalized subjects, V2
Visit	Sanooning	V1	V2	V2	VA	V5	DT1	DT2	DT23	and V4 assessments will be done at home. (X) is for V2 and V4 assessments for hospitalized subjects.
V ISIL	Day_1 to	V I	¥ 2	3	V 4	$\frac{\sqrt{3}}{5(+1)}$	0	112	$\frac{113}{28(+4)}$	
Day	Day 1 Day 1	1	2	$(\pm 1)^4$	4	$EOT^5$	(±1)	(±2)	$EOS^5$	Notes  ; Protocol Section

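### ECG intervals are listed but not summarised by treatment group, and the timing of the Visit 5 ECG relative to dose is not stated

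*SAP*

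**What the plan says.** SAP 4.14.4 reads in full: "Screening and Day 5 ECG data will be provided in data listings". Protocol 11.5.6 matches it: "Screening and subsequent ECG data will be provided in data listings". Neither document gives an interval summary, a change from baseline or a count of abnormal readings.

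The data would support more than a listing. Protocol 8.5 strongly prefers a 12-lead machine that "calculates heart rate and measures PR, QRS, QT, RR, and QT interval corrected for heart rate according to Fridericia (QTcF) intervals". The schedule in SAP 7.1 allows a fallback: "12-lead ECG strongly preferred but where not possible, 6-lead ECG may be performed". ECGs are marked at Screening and Visit 5 (Day 5 ±1) only.

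Other safety measures are treated differently. SAP 4.14.2 gives laboratory values observed, change-from-baseline and shift summaries. SAP 4.14.3 gives vital signs, including heart rate, observed and change-from-baseline summaries. SAP 4.1 presents safety tables by actual treatment group for Part 1, Part 2 and pooled, and by age group for the pooled data.

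On timing, protocol 8.5 says: "If blood sampling and a nasal swab are scheduled for the same timepoint as ECG recording, those assessments should be done after the ECG". For the swab, protocol 8.12 says: "Samples should be taken at approximately the same time each day before study drug administration". The PK sample in protocol 8.13 is listed as "Visit 5: predose" for hospitalized and non-hospitalized children alike.

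**The concern.** Protocol 2.2.1 and SAP 3.2.1 make safety and tolerability compared with placebo a primary endpoint of Part 1, and the measures they name are not exhaustive. This is the first paediatric study of the drug, and the protocol gives cardiac findings particular attention. The screening ECG must be reviewed before dosing, cardiac biomarkers are drawn where blood volume allows, and "All subjects with new abnormal cardiac laboratory values or abnormal ECG results after receiving study drug should have echocardiograms".

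A listing helps to find an individual child with a striking ECG. It is poor at showing a modest shift across a group. Between Screening and Day 5 these children are recovering from an acute infection, so fever and heart rate may change and intervals may change with them. The placebo arm is the control for that, and a listing makes no summary use of it.

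Timing is the second issue. If most Visit 5 ECGs are recorded before that day's dose, a report that finds nothing on ECG describes recordings made about a day after the previous dose. The reader should be told so.

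**Working it through.** **1. Group sizes (SAP 4.2; allocation ratios from SAP 2.1).**
- Part 1: 2 age groups × 2 cohorts × 12 = 48, at 2:1, giving 32 EDP-938 and 16 placebo.
- Part 2: 2 age groups × 20 = 40, at 4:1, giving 32 and 8.
- Total: 48 + 40 = 88, which agrees with the stated figure of approximately 90. Pooled arms: 64 and 24.
- One age group, Parts 1 and 2 pooled: 16 + 16 = 32 and 8 + 4 = 12.

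**2. Precision of a by-arm comparison.** The documents give no SD for change in QTcF, so 15 to 25 ms is an assumption. The 95% CI half-width for the difference in mean change is 1.96 × SD × √(1/n₁ + 1/n₂).

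| Data | n₁, n₂ | √(1/n₁ + 1/n₂) | SD 15 ms | SD 20 ms | SD 25 ms |
|---|---|---|---|---|---|
| Pooled | 64, 24 | 0.239 | 7.0 | 9.4 | 11.7 |
| Part 1 | 32, 16 | 0.306 | 9.0 | 12.0 | 15.0 |
| One age group, pooled | 32, 12 | 0.339 | 10.0 | 13.3 | 16.6 |
| Part 2 | 32, 8 | 0.395 | 11.6 | 15.5 | 19.4 |

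These figures assume an evaluable ECG pair for every child and combine all EDP-938 doses. Missing ECGs would widen them.

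**3. What the passages imply about ECG timing.**
- Protocol 8.5 puts the swab and blood draw after the ECG when they share a timepoint. Protocol 8.1 and note 6 of the schedule recommend the order ECG, vital signs, swab, blood.
- Protocol 8.12 puts the swab before study drug. Protocol 8.13 makes the Visit 5 PK sample predose, at about the time of the swab.
- Protocol 7.1.3 says non-hospitalized children should be dosed at the clinic on Day 5.

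Taken together, these place the Visit 5 ECG before the Day 5 dose, roughly 24 hours after the Day 4 dose. No ECG is scheduled with the only postdose PK sample, at 3 hours on Day 1.

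This is an inference. The sequence in 8.1 is a recommendation, the rule in 8.5 applies only to a shared timepoint, and on-site dosing is qualified elsewhere by whether it is possible. A child dosed before arriving, or attending an end-of-treatment visit within 24 hours of the last dose after stopping early, could have an ECG at another time after dosing.

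**The case against.** The strongest reply is that the two documents agree, so listing ECGs is a deliberate reporting choice and not an inconsistency. The readings are single, taken locally on 12 or 6 leads, and reviewed for gross abnormalities and intervals of concern, a purpose that a listing serves. ECG is not named in the Part 1 safety endpoint. Protocol 1.4 and 4.4.2 report no pattern of ECG change and no clinically significant ECG findings in the adult challenge study. All of this stands, and it limits the weight of the point. It does not explain why continuous interval data should have less summary than vital signs.

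A reader might go further and infer that the trial looks for an ECG effect only at trough and never compares it with placebo. The documents do not support that.
- On timing, no passage states that the Visit 5 ECG is predose, whereas the protocol says so explicitly for the swab and the PK samples.
- Trough is also not absence of exposure: adult 24-hour concentrations after once-daily dosing were about 14.5 to 25 times the in vitro EC90 (protocol 4.4.2).
- On comparison, heart rate is summarised by arm as a vital sign, and ECG abnormalities recorded as adverse events enter the by-arm tables. The IDMC sees unblinded safety data, and the listings are sorted by treatment group.

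What remains is that PR, QRS, QT and QTcF have no planned summary by arm.

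The pooled precision is also the most favourable case. Part 1, whose primary endpoint is the reason for the concern, gives about ±9 to ±15 ms.

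**Conclusion.** The point holds as a gap in reporting. The plan collects ECG intervals at two scheduled times in a placebo-controlled study and summarises none of them by arm, so a systematic shift within normal limits would not be summarised. A pooled comparison would have a half-width of about 7 to 12 ms. That rests on the assumed SD, complete ECG pairs and pooling of parts, ages and doses. It would be descriptive, in keeping with a study that plans no formal hypothesis testing for Part 1 or Part 2.

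The timing point is narrower. ECG time relative to dose is not stated, and the procedural order suggests that the Visit 5 recording usually comes before the Day 5 dose. This affects how a negative ECG finding should be read. It does not establish that every recording is at trough.

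The documents state no confirmed cardiac harm. The juvenile toxicity section is not readable in the public version, so nothing is concluded from it.

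**What to change.** In SAP 4.14.4, add one descriptive table for heart rate, PR, QRS and QTcF, with observed values and change from Screening to Day 5. Add counts of treatment-emergent readings judged abnormal and clinically significant. Present it by actual treatment group for Part 1, Part 2 and pooled, and by age group for the pooled data, as SAP 4.1 does for other safety tables. A 95% CI for the pooled arm difference is optional and should be labelled descriptive, since the other safety summaries have none.

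The sponsor should reconcile protocol 8.1, 8.5, 8.12 and 8.13 and state the intended timing of the Visit 5 ECG relative to dose. The report should give ECG time relative to last dose where available. No change to ECG timing is proposed here.

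The cost is one table from ECGs already scheduled. Its main limit is the source: single, locally read 12- or 6-lead recordings. One check is needed first. Protocol 8.5 mentions recording the clinical interpretation only on a hard copy, so the sponsor should confirm that the interpretation and the intervals are both in the database.
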